 - g. any current chronic medication (previous 6 months or longer) for asthma
 - h. any current chronic medication (previous 6 months or longer) for hypertension
5. History of chemotherapy; history of radiotherapy to the abdomen or pelvic area.
6. History of tubal surgery or significant tubal adhesions.
7. Endometriosis \geq AFS Stage III.
8. History of myomectomy (abdominal), ovarian cystectomy, or unilateral oophorectomy, unless subsequent laparoscopy indicates the absence of significant pelvic adhesions.

Exclusion Criteria For Males

1. Previous IVF, GIFT, ZIFT or TET (ovulation induction) with the current partner.
2. Previous intrauterine insemination.
3. Vasovasostomy ever.
4. Varicocelectomy within previous 6 months.
5. History of pelvic node dissection.

All recommendations by the RMUs about eligibility will be reviewed by the DCC, which will meet weekly to make the final determination. Questions about eligibility that arise early on in the course of screening a particular couple can be referred to the DCC for an early decision.

Section 4. METHODS OF RECRUITMENT AND RANDOMIZATION

A. Methods of Recruitment

Each of the participating centers in the National Reproductive Medicine Network operates a large, multifaceted clinical service and serves as a referral center for couples with a variety of reproductive disorders. In about ten percent of couples completing a thorough infertility investigation, no apparent explanation is found for their failure to conceive (unexplained infertility). In 40-50 percent of infertile couples, male factors are found to be abnormal; in about half of these (20-25 percent) the female partner appears to be normal and an abnormal male factor is the only apparent problem (pure male factor infertility). While these two diagnoses are reasonably common, many of those diagnosed will already have received treatment. Such treatment failures represent a group with lower fertility potential. To minimize potential selection bias, only couples who have received no prior treatment with hMG or intrauterine insemination will be eligible for randomization. In addition, efforts will be made to recruit subjects through physicians in the medical community surrounding each center. Participating community physicians would bill for the diagnostic workup in the usual fashion but must agree to follow a standardized protocol for tests and diagnoses.

Attempts to establish a network of community physicians (ideally, sufficient to refer 60 couples per year in whom the female appears to be normal) have been made by several RMUs using the following approaches:

- 1) Personal contact between the research center and community physicians, by letter (on either center or network letterhead), describing the protocol, its benefits and risks.
- 2) Presentations at hospital departmental meetings, Grand Rounds, or other educational meetings focusing on treatment options for infertile couples.
- 3) News releases (print, radio, television media) describing the Network in general

and perhaps the study in particular, including its purpose, selection criteria, and potential benefits to eligible couples.

- 4) Satellite clinics contracted by the RMU where patients will be recruited, evaluated and treated, with the understanding that all semen evaluations and inseminations must be performed at the RMU.

Recruitment of subjects from the community at large must be done carefully, both to insure standardization and to avoid any appearance of shunting patients away from the physicians' private practices. At the same time, the establishment and funding of the National Reproductive Medicine Network is a newsworthy event. A news release focusing on the Network in general, its makeup, and the types of problems it intends to study, should be designed to introduce the Network in a non-threatening way. (The Office of Public Information at each medical center may be able to help with this.) The release should conclude with a brief "for example" look at this study, the Network's first. No overt recruitment appeal should be made, but a telephone number should be provided at the end of the release for couples or physicians desiring further information. Local infertility support groups may be able to help with dissemination of information. All inquiries will be answered by the local center's Research Nurse. An "information sheet" describing the National Reproductive Medicine Network will be developed for distribution. As specific research protocols are developed, suitable information sheets for each will be developed.

Emphasis will be placed on the potential benefits of participation to eligible couples, including:

- a) Access to "state of the art" therapy, i.e., the latest standardized techniques for assessing the etiology of infertility, for performance of IUI and ICI, for timing insemination, or for stimulating the recruitment and ovulation of multiple oocytes.
- b) Contribution to medical knowledge.

B. Phase of Infertility Workup at Recruitment

The diagnostic workup will be completed before a couple becomes eligible to enter the study. For this reason it is clearly essential to define the testing protocols and diagnostic criteria clearly and explicitly. We will insure agreement and adherence to these standards by conducting quality control studies on portions of the infertility workup following initial recruitment. Appendix B contains a description of quality control protocols related to enrollment, treatment procedures, data forms and laboratory tests. As mentioned previously, community physicians and satellite clinics providing patients will be asked to use the same definitions, testing protocols, and diagnostic criteria that will be used at the RMUs. If there is documentation in the medical record of the post-coital testing, hysterosalpingogram, laparoscopy and endocrine evaluations, these results will be used for diagnosis. The endometrial biopsy may be performed elsewhere but slides should be available for review at the RMU. On-site semen collection is encouraged but not required. Semen evaluations and antisperm antibody immunobead tests will be performed at the RMUs and quality control procedures will be established to insure the uniformity of laboratory assessments across sites. The University of California, Davis has agreed to review any borderline results on the antisperm antibody tests.

C. Randomization

From the scientific and ethical standpoints, infertile couples in whom the female partner appears to be normal may be randomly assigned to any of the four treatment blocks of this study; i.e., there are no convincing data from existing controlled studies that any of the proposed regimens is superior for treating these couples. Couples will be counseled by the Research Nurse at the RMU regarding risks and benefits of all treatment blocks. At the time of counseling, it will be emphasized that those randomized to "no hMG" will be offered up to four cycles of hMG treatment at the end of the trial if they have not already conceived.

All subjects will be asked to sign an informed consent to participate in the study (see Appendix A). Only those eligible couples who are willing to accept randomization can be enrolled in the trial.

The randomization procedure will stratify on RMU, i.e., each RMU will have its own independent randomization schedule. Permuted blocks of size four or eight will be employed within each RMU.

The DCC will review the relevant enrollment forms and will respond to the RMU with a decision on eligibility and, where appropriate, a randomization assignment. If the forms are incomplete or the documentation inadequate, the RMU will be notified; members of the DCC will meet weekly to review and resolve all such questionable cases. As part of quality assurance, the DCC will double check, in detail, on eligibility information for a randomly selected 4% of subjects, by requesting the entire medical record for review.

Section 5. MEASURES OF EFFICACY AND ADVERSE EFFECTS

[figure not shown]
A. Specific Measures of Efficacy

The relevant measure of treatment efficacy for this study is pregnancy, which will be determined by a standard protocol as outlined in Figure 2 below.

Ovulation will be taken to be the day of insemination, i.e., the day after a morning LH surge for women in the spontaneous ovulation groups, and the day corresponding to 36 hours after administration of hCG in the hMG-stimulated groups.

If menses does not occur by luteal day 14 (around cycle day 28-29), a blood sample will be drawn on luteal day 15 for serum β -hCG and the test will be repeated in two days (irrespective of whether menses begins in the interim) to evaluate whether β -hCG is rising (Romero et al., 1986). If the β -hCG is rising and if menses have not occurred, β -hCG will be repeated on luteal day 21 and a transvaginal ultrasound will be performed. This corresponds to the day that a gestational sac can usually first be seen by transvaginal ultrasound (Fossum et al., 1988). If no sac is seen, the β -hCG and ultrasound will be repeated four days later. Vaginal bleeding that occurs between the second β -hCG assay and the scheduled ultrasound will be evaluated by RMU physicians for possible miscarriage or ectopic pregnancy according to standard clinical practice.

Figure 2. Evaluation of Efficacy and Adverse Effects of Treatment

CYCLE 2

Two or more follicles on Cycle 1
Repeat Cycle 1 protocol

One follicle on Cycle 1
Increase hMG dose to 4-amps/day

No follicles on Cycle 1
Increase hMG dose to 4-amps/day

*If at any time U/S shows more than 6 follicles with diameters ≥ 18 mm or E2 reaches ≥ 3,000 pg/ml, do not give hGG and do not inseminate. EXIT TREATMENT CYCLE AND SKIP NEXT CYCLE. RE-EVALUATE BEFORE CONTINUING TREATMENT.

Using the above protocol to monitor early pregnancy, a continuum is seen with different pregnancy outcomes defined as follows:

- 1) **Preclinical abortion:** serum β -hCG > 10 mIU/ml on luteal day 15 (cycle day 29-30) and a higher serum β -hCG on luteal day 17, but no gestational sac seen subsequently by ultrasound.
- 2) **Clinical abortion:** Occurrence of a spontaneous abortion after a gestational sac is seen, but before 20 completed weeks gestation estimated from LMP (i.e., less than 18 weeks post-insemination).
- 3) **Preterm delivery:** Delivery between 20 and 37 weeks gestation estimated from LMP (i.e., 18 to 35 weeks post-insemination).
- 4) **Term delivery:** Delivery after 37 completed weeks of gestation estimated from LMP (i.e., after 35 weeks post-insemination).

Other pregnancy outcomes will be determined, e.g., presence of multiple pregnancy at the time of early ultrasound exam (five weeks after insemination, seven weeks after last menstrual period, or when the serum β -hCG reaches 2,000 mIU/ml by IRP) and at delivery; ectopic pregnancy; and presence of congenital anomalies at delivery.

B. Specific Measures of Adverse Effects

Adverse effects may be considered for 1) method of insemination, and 2) method of ovulation induction. For each, adverse effects may be assessed a) subjectively, and b) objectively.

1. Method of Insemination (IUI or ICI)

a) Subjective Evaluation

A structured questionnaire has been developed to evaluate the patient's overall level of satisfaction/dissatisfaction with the assigned method of insemination, as well as the presence or absence of specific symptoms during/following insemination. More specifically, it measures that patient's feelings regarding the time required to perform the insemination and the degree of pain or cramping associated with the procedure.

Patients who drop out will be asked to complete a separate questionnaire asking them to indicate which of a list of potential factors played a role in their decision to drop out, and to rank those factors from most to least influential. The factors include: cost, time/inconvenience, and side effects.

b) Objective Evaluation

Few, if any, measurable adverse effects are expected from either ICI or IUI. Patients will be asked to call the Research Nurse for temperature elevations $> 100^{\circ}\text{F}$. In general, patients will be evaluated clinically to ascertain subclinical pelvic inflammatory disease (PID). Patients will be counseled regarding the possibility of PID in an insemination cycle, and will be given a specific set of guidelines concerning when to call the Research Nurse.

2. Method of Ovulation Induction

a) Subjective Evaluation

Each questionnaire will evaluate the level of satisfaction with the time required for monitoring treatment with hMG/hCG, and the degree of discomfort experienced with parenteral injections, with venipunctures, and with ultrasound exams. Each patient will be asked to indicate the presence or absence (and degree) of symptoms such as abdominal pain

or discomfort, abdominal distension, bloating, weight gain, nausea, vomiting, diarrhea, headache, pain at injection sites, etc.

Patients who drop out of treatment will be asked to complete a questionnaire asking them to indicate and rank those factors that played a role in their decision. The list of factors include cost, time/inconvenience, requirement for parenteral medication, requirement for repeated venipuncture, requirement for ultrasounds, and concern regarding side effects (multiple gestation, hyperstimulation syndrome).

b) Objective Evaluation

1) All patients

Within 12 to 14 days after insemination, clinical criteria will be used to ascertain those patients with greater than mild hyperstimulation. Each woman will be asked whether she has experienced a weight gain of more than 10 pounds. Those reporting weight gain will be evaluated for evidence of severe hyperstimulation. The following laboratory measures and clinical criteria will be considered:

a) Ovaries > 10 cm in maximum diameter

b) Evidence of marked hemoconcentration:

1. Significant rise in hemoglobin or hematocrit > 15%
2. Evidence of electrolyte imbalance
3. Evidence of ascites or pleural effusion
4. Evidence of hypervolemic shock
5. Evidence of hypercoagulable state
6. Decreased urine output

The number of patients (cycles) requiring such workups, and the number meeting criteria for severe hyperstimulation, will be recorded. Most patients will not require such testing; in asymptomatic subjects no special effort will be made to evaluate ovarian size or to measure hematologic parameters following the hCG injection.

2) Patients Who Conceive

Data will include the rates of multiple gestation, preclinical abortion, clinical abortion, preterm delivery and term delivery, and eventual pregnancy outcome (including the incidence of congenital anomalies). A sonogram will be obtained five weeks after insemination or seven weeks after the last menstrual period, or when the serum β -hCG reaches 2,000 mIU/ml by IRP. Thereafter, the Research Nurse will contact the patient's obstetrician every three months to gather information on the course of the pregnancy. Obstetrical and newborn records will also be obtained after delivery.

Section 6. DATA TO BE COLLECTED AND FORMS TO BE COMPLETED

Data collection forms have been developed in two broad categories: pre-randomization forms and post-randomization forms. An initial questionnaire is provided to screen out couples who are ineligible on the basis of age, prior treatment, or relevant surgery. Those who pass the screen complete recruitment questionnaires and other pre-randomization forms (some of which will involve abstracting information from medical records) to determine a couple's eligibility for the trial and willingness to participate. In addition, they provide baselines against which change can be assessed. Once a couple is disqualified, there is no need to complete any of the subsequent pre-randomization forms. We have also included a form for recording data on ineligibles as well as on couples who refuse to participate.

Each week, the DCC will upload all completed recruitment questionnaires, diagnostic test abstracts and enrollment summaries from each RMU. The DCC will review the data and send an eligibility determination form back to the RMU for each couple. If the information is complete and the couple is eligible, this form will also include the randomization assignment.

The post-randomization forms include: forms for documenting treatment administration and for monitoring treatment response; forms for documenting outcomes of treatment; forms for subjective and objective evaluations of treatment, including adverse reactions and side effects; and a form for documenting any drop-outs/ withdrawals. The treatment forms are arranged as a set, with one set covering one cycle. They have been designed in the hope that they may serve as case notes in the RMU medical charts in order to reduce the amount of record-keeping required of clinical personnel. In addition, we have included a first cycle questionnaire for each partner that can be completed while waiting for the insemination procedure. While all of the other forms have been limited to items that are needed to accomplish the research goals of the trial, these "waiting room" questionnaires include

variables that are not strictly needed but are certainly of interest and would be useful for ancillary studies.

Table 3 lists the forms by category and name and indicates those that are to be completed by clinical staff at the RMU, by the study subjects (*) or by DCC personnel (**).

TABLE OF DATA COLLECTION FORMS

FORM #	LABEL	DESCRIPTION
--------	-------	-------------

FORMS FOR INITIAL RECRUITMENT OF POTENTIAL PARTICIPANTS

- | | | |
|----|------|--|
| 1. | None | LOG BOOK: LIST OF POTENTIAL PARTICIPANTS |
| 2. | SC | INITIAL SCREENING FOR ELIGIBILITY |
-

PRE-RANDOMIZATION FORMS: ELIGIBILITY DETERMINATION

QUESTIONNAIRES:

3. WOMAN'S RECRUITMENT QUESTIONNAIRE:

WR1	1. DEMOGRAPHIC, REPRODUCTIVE/CONTRACEPTIVE HISTORY, OTHER INFERTILITY TREATMENTS
-----	--

WR2	2. PREGNANCY HISTORY
-----	----------------------

4. MAN'S RECRUITMENT QUESTIONNAIRE:

MR	1. DEMOGRAPHIC, REPRODUCTIVE HISTORY, SURGICAL AND MEDICAL HISTORY
----	--

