All couples who are randomized will be included in the statistical analyses, regardless of treatment outcome or completion of all four study cycles. Differences across RMUs and confounding variables such as age and duration or degree of infertility (primary or secondary) will be considered in the analysis. A detailed description of the protocol for the trial is given in Section 3 below.

Section 3. DETAILED DESCRIPTION OF THE STUDY

A. Study Objectives

This study addresses the question of whether superovulation with hMG, IUI, or the combination of hMG/IUI increases the likelihood of conception in infertile couples when the female partner appears to be normal. Because of the arbitrary nature of cutpoints for differentiating normal from abnormal semen quality, the protocol has been revised to allow all males with any motile sperm to be entered into the trial.

B. Study Design

A 2-factor design will be used as diagrammed below:

	IUI	ICI
hMG		
No hMG		

Infertile couples will be recruited from patients with a well-documented diagnosis of unexplained infertility in the female, regardless of the values for semen quality in the male, according to criteria described below in Section 3E. Eligible couples will be randomized to one of the four treatment arms represented by the cells in the above fourfold table using a random number scheme described below in Section 4C. Treatment will continue until pregnancy is achieved or until four treatment cycles are completed without pregnancy. Women who do not demonstrate adequate ovarian response to increasing levels of hMG stimulation during the first two treatment cycles will be included in the analysis as treatment failures, but will not undergo additional treatment in the study.

C. Procedures

1. hMG protocol

As outlined in Figure 1 below, women randomized to one of the two hMG treatment arms will have a baseline transvaginal ultrasound (U/S) examination on or before day 3 of the menstrual cycle. In carrying out the hMG protocol, the criteria for estradiol level and follicle size can be adjusted within a $\pm 10\%$ range to allow for measurement error and clinical judgement. All other instructions are to be followed to the letter and the $\pm 10\%$ margin should be adhered to strictly.

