If at any time U/S shows more than 6 follicles with diameters ≥ 18 mm or E2 reaches $\geq 3,000$ pg/ml, do not give hCG and do not inseminate. EXIT TREATMENT CYCLE AND SKIP NEXT CYCLE. RE-EVALUATE BEFORE CONTINUING TREATMENT.

be performed 36-40 hours after hCG administration. Couples will be advised to abstain from intercourse for 72 hours following the insemination in order to insure that any conceptions occurring in that cycle are actually the result of the treatment.

Women who develop only one follicle measuring ≥ 18 mm by cycle day 15 (i.e., after 12 days of hMG stimulation) will receive hCG on day 15 and undergo insemination as above, but will commence the next cycle (unless pregnancy occurs) with 4 amps per day of hMG. In all other respects they will follow the above protocol for hMG administration and monitoring.

Women who show no follicle development by cycle day 15 will not receive hCG or insemination, but will commence the next cycle with 4 amps per day of hMG. If criteria for hCG administration are not reached on this high-dose hMG regimen, no further attempts at ovarian stimulation will be provided as part of the study.

At any time, if more than 6 follicles measuring ≥ 18 mm (range 16.2-19.8 mm) are seen by U/S or if E_2 reaches $\geq 3,000$ pg/ml (range 2700-3300 pg/ml), no hCG will be given and no insemination will be done. No treatment will be given during the following menstrual cycle but the woman will be monitored. If conception occurs, the pregnancy will be followed in the same way as all other study pregnancies. If menses occurs, the woman may re-enter the trial during the subsequent cycle provided that the transvaginal U/S on cycle day 3 indicates both ovaries are < 10 cm (range 9-11 cm) on all diameters [or the absence of ovarian follicular cysts > 3 cm (range 2.7-3.3 cm)]. To prevent a repeat occurrence of hyperstimulation, subsequent treatment cycles should be conducted using a "step-down" administration of hMG, as follows: 3 amps of hMG for 2 days, then 1 amp daily.

After a rest cycle taken for personal reasons rather than a clinical indication, a woman may re-enter treatment only if menses occurs.

2. Spontaneous ovulation monitoring protocol

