Women who are not randomized to hMG stimulation will undergo insemination (IUI or ICI) timed to their spontaneous ovulation. The day of expected ovulation will be determined by averaging the length of previous menstrual cycles and/or by charts of basal body temperature. Beginning four days prior to expected ovulation, a woman will test for an LH surge using an OvuQuick (Quidel Inc) urinary dipstick. This urinary LH test will be performed daily, using the second void of the morning, until an LH surge is detected. Beginning two days prior to expected ovulation, couples will be instructed to abstain from vaginal intercourse and the male will be instructed not to ejaculate until the insemination sample is obtained. Insemination (IUI or ICI) will be performed on the day after the LH surge, between 9:00 a.m. and 3:00 p.m. If an LH surge is not detected, the woman should stop testing after 9 days. On cycle day 24 (range: days 22-26), a serum progesterone level should be obtained to determine whether she has ovulated. A women must exit the study if she has 2 documented anovulatory cycles.

3. IUI protocol

Washed sperm will be prepared using the following procedures. Semen specimens will be collected at the clinical site by masturbation after at least 48 hours of abstinence, and will be allowed to liquify at room temperature. Evaluation and preparation of the semen will begin within one hour of collection. A 0.07 ml aliquot of the semen will be analyzed for sperm concentration, percent motility and progression; slides will be made for sperm morphology assessment and video recordings will be made for subsequent CASA. Viscous samples will be mechanically dispensed by repeating passage through a sterile 15 gauge hypodermic needle attached to a sterile hypodermic syringe. The remaining semen will be transferred to a 15 ml Falcon conical tube. If the semen volume is greater than 5 ml, the sample will be divided equally between two 15 ml tubes. The semen will be diluted 1:2 (V/V) with medium. The

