Every six months, the DCC will provide the Steering Committee with aggregate summaries of the data collected to date. On the recommendation of the DSMB, which will

have access to data broken down by treatment group, the Steering Committee will decide whether to continue the study or to terminate it. These decisions will seriously affect the operating characteristics of the study (significance level and power), and should therefore be made according to rules developed for performing interim analyses of accumulating data (Friedman et al., 1985: Chapter 15; Pocock, 1983: Chapter 10).

The possibility must be entertained that one of the experimental treatments is less effective than the control. If this seems to be the case based on the interim data, and if harm to the patient is possible, the Steering Committee should be encouraged to decide on early termination of that treatment arm with less persuasive evidence than required for early termination with a positive conclusion (Lan and Friedman, 1986). That is, the Steering Committee might decide to drop an investigational regimen with the conclusion that it may be poorer than the control if the p-value for the test comparing the two is 0.15 or less.

The most widely used procedure for performing several interim statistical analyses while holding the overall significance level at the usual value (0.05 or 0.01) is the one due to O'Brien and Fleming (1979). This procedure will be adopted for interim analyses aimed at testing for efficacy.

E. Methods of analysis

The unit of analysis will be the couple, and the primary response variable will be a binary one: success if the woman conceives while in the study versus failure if not. The most important principle underlying the statistical analysis will be the intention-to-treat principle. It is characterized by the aphorism "If randomized, analyzed": a couple who has been randomized to a treatment group is analyzed along with all other couples so randomized, even if they were minimally compliant. This principle leads to a likely underestimation of a

treatment's effect, but the alternative of removing minimally compliant or noncompliant couples could lead to the worse bias of overestimating its effect. For example, a couple's decision to discontinue complying with the assigned treatment regimen might be due to a perceived lack of efficacy. The withdrawal of such a couple from analysis could result in an overestimation of that treatment's effectiveness.

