The primary statistical analysis will consist of separate comparisons of each experimental treatment's success rate versus the control's after stratifying on RMU using the Mantel-Haenszel chi-square procedure (1959). If other variables measured at baseline are found to be distributed very differently in different treatment groups (the criterion for "very different" might be statistical significance at the 0.10 or 0.20 level), they would be adjusted for statistically, either by post-stratification (using the Mantel-Haenszel procedure) or by regression control (using logistic regression modeling) in a secondary, confirmatory analysis. Given the likelihood that these variables will be only slightly correlated with response, the results of the secondary analysis will almost surely confirm the results of the primary one, with respect both to the direction of the difference between the treatments and to its statistical significance or nonsignificance. In the extremely unlikely event that the results of the primary and secondary analyses are contradictory, there would be little if any credibility to any attempted definitive inference from the study.

References

4. Daly DC. Treatment validation of ultrasound-defined abnormal follicular dynamics as a cause of infertility. *Fertil Steril* 1989; 51:51.

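### The 72-hour abstinence advice after insemination is written for the hMG arms only, so three of the five comparisons are open to a differing co-intervention of unknown size

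*Protocol*

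**What the plan says.** Section 3.C.1 (hMG protocol) opens by fixing its scope: "women randomized to one of the two hMG treatment arms will have a baseline transvaginal ultrasound". Apart from a 10% tolerance on estradiol and follicle size, it is strict: "All other instructions are to be followed to the letter". After describing the single insemination it adds: "Couples will be advised to abstain from intercourse for 72 hours following the insemination". The reason given is that conceptions in the cycle should be attributable to the treatment.

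Section 3.C.2 (spontaneous ovulation monitoring) covers the two arms without hMG. It restates the rule for the days before insemination: couples abstain from two days before expected ovulation and "the male will be instructed not to ejaculate until the insemination sample is obtained". It says nothing about the period after insemination and does not refer back to 3.C.1.

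Sections 3.C.3 (IUI) and 3.C.4 (ICI) serve all arms. They require 48 hours of abstinence before semen collection and 10 minutes supine afterwards, and say nothing on later intercourse. The quality-assurance list in Appendix B, Section 2.3, covers abstinence before treatment only.

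Section 5.A sets the timing: "Ovulation will be taken to be the day of insemination". Section 9.E defines the endpoint as "success if the woman conceives while in the study versus failure if not", and compares success rates "after stratifying on RMU using the Mantel-Haenszel chi-square procedure".

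**The concern.** The reason given for the rule applies equally to all four arms, yet the rule is written for two. The pre-insemination rule appears in both 3.C.1 and 3.C.2 in nearly the same terms, so a rule meant for both groups was elsewhere written out twice. This looks like a drafting omission, but a site following the text would advise the two groups differently.

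The difference falls exactly along the hMG factor, and the 72 hours begin on the assumed day of ovulation. The endpoint has no attribution rule, so a conception from intercourse after insemination counts as a success for the assigned arm. The planned adjustments, for RMU and for unbalanced baseline variables, cannot remove a difference that arises after randomisation. If couples without hMG do have more intercourse in this window, their conception rate would most likely rise and the apparent hMG effect shrink. A real hMG benefit could be missed.

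**Working it through.** **Which comparisons are exposed.** Section 3.D lists five.

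| Comparison | 72-hour advice, first arm | 72-hour advice, second arm | Exposed |
|---|---|---|---|
| hMG/ICI v ICI | yes | no | yes |
| hMG/IUI v ICI | yes | no | yes |
| hMG/IUI v IUI | yes | no | yes |
| IUI v ICI | no | no | no |
| hMG/IUI v hMG/ICI | yes | yes | no |

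**The plan's own figures (Section 3.D).** Inputs: control rate 0.075, experimental rate 0.1875, two-sided level 0.01 (critical ratio 2.576), 210 couples per arm. Power by the pooled-variance normal approximation, without continuity correction, is

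Φ{ [d − 2.576·√(2p̄(1−p̄)/n)] / √([p₁(1−p₁)+p₂(1−p₂)]/n) }, with d = p₂ − p₁ and p̄ = (p₁+p₂)/2.

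Here d = 0.1125 and p̄ = 0.13125. The two standard errors are 0.03295 (pooled) and 0.03249 (unpooled). So (0.1125 − 2.576×0.03295)/0.03249 = 0.85 and power is 80.2%. The matching sample size is 209 per arm, against 210 stated. For 0.10 v 0.20 the same formula gives 61.7%, against 62% stated. The plan's figures reproduce and are not in dispute.

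**Illustration of a difference.** The protocol gives no rate of conception from intercourse after insemination, so the size cannot be derived. The values below are assumptions: 0.5, 1 or 2 percentage points per couple over up to four cycles. Two readings of the planned 7.5% are possible:

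- (A) 7.5% is the control rate under abstinence, so unrestricted intercourse raises control above it.
- (B) 7.5% already includes ordinary intercourse, so abstinence lowers the hMG rate below 18.75%.

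| Assumed difference | (A) control v 18.75% | Power | (B) 7.5% v hMG rate | Power |
|---|---|---|---|---|
| 0 | 7.5% | 80% | 18.75% | 80% |
| 0.5 points | 8.0% | 75% | 18.25% | 77% |
| 1 point | 8.5% | 69% | 17.75% | 72% |
| 2 points | 9.5% | 56% | 16.75% | 63% |

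**If hMG has no true effect.** Set the hMG rate to 7.5% and control to 8.0, 8.5 or 9.5%. The chance of a significant result against hMG rises from the nominal 0.5% (half of 0.01) to 0.9, 1.4 or 3.3%.

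**How large the assumptions are per cycle.** A rate of 7.5% over four cycles is 1 − 0.925^(1/4) = 1.93% per cycle. Rates of 8.0, 8.5 and 9.5% correspond to 2.06, 2.20 and 2.46% per cycle. The assumed differences are therefore 0.13, 0.27 and 0.53 points per cycle, or 7, 14 and 28% of the base rate.

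**The case against.** The strongest reply is that this is one misplaced sentence, not a difference between arms. It speaks of couples in general, it directly follows a description of insemination by either route, and its reason fits every arm. Nothing exempts the arms without hMG. Day-to-day instructions are left to the Procedures Manual, and the consent form would also be a natural place for this advice; neither is available here, and either may give the rule to everyone. Couples are only advised to abstain afterwards, whereas beforehand they are instructed, so adherence in the hMG arms is unknown too. The strictness clause mainly contrasts clinical tolerances with other hMG instructions. Nothing in the protocol shows that intercourse after insemination adds conceptions, and the 2-point case needs a 28% relative rise in per-cycle conception.

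Most of this stands as a limit on what can be claimed. All-arms intent is plausible, no difference in behaviour is shown, and the power figures are not estimates. None of it makes the protocol consistent, though: as written, the rule applies to half the arms. If it was meant for all four, the correction simply records that intent.

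**Conclusion.** The concern holds as a fault in the protocol text. A rule with a reason common to all arms is stated only for the hMG arms, and three of the five comparisons are open to a co-intervention that may differ between them. It should be fixed, but it is not shown to have biased anything.

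The size is unknown. If behaviour after insemination does not differ between arms, or such intercourse adds no conceptions, there is no effect. With a low control rate, small shifts would matter: an assumed 1 point per couple takes power from 80% to 69% or 72%, depending on the reading of the planned 7.5%. The direction is an inference: any bias would probably run against hMG, so it could mask a benefit but would not be expected to create one. Confidence is medium, because the consent form and Procedures Manual may already carry the rule for every arm.

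**What to change.** Move the 72-hour sentence from Section 3.C.1 into Sections 3.C.3 and 3.C.4, so that one identical instruction after insemination applies to all four arms. Check that the consent form and Procedures Manual say the same. If the insemination summary form (IN) does not already record it, add an item on intercourse in the 72 hours after insemination, so that any remaining difference between arms can be described.

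The cost is one sentence moved and at most one item on an existing form. The 210 couples per arm, the 0.01 level and the planned tests stay as they are.
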